In addition to establishing the benefits of exercise training in people with 'watch and wait' CLL, this study provides a unique methodological model to investigate the effects of exercise on neoplastic activity in humans. Given that CLL tumour cells are highly abundant in peripheral blood (>5000 cells/ul) and thus easily and relatively non-invasively accessible, and the absence of confounding therapies (e.g. anti-cancer therapy), that are typical of other cancer diagnoses, people with 'watch and wait' CLL provide a unique model to prospectively assess the short-term effects of exercise training on tumour cell mass and activity *in vivo*, and in doing so conduct mechanistic investigations to discover how regular exercise averts tumour growth in humans. A number of anti-tumour mechanisms of exercise have been proposed, including immune function, inflammation, adipose tissue and metabolic hormones (McTiernan, 2008), which will be explored as secondary outcome measures in our study herein.

Accordingly, this study aims to confirm the safety and acceptability of an exercise programme in people with 'watch and wait' CLL, as well as preliminarily explore the effects of exercise training (pre-intervention to post-intervention) on tumour cell mass (CLL tumour cell frequency) in peripheral blood. The aforementioned data will be used as preliminary data for a power calculation, for a future larger randomised control trial. Additionally, this study will enable preliminary assessment of changes (pre-intervention to post-intervention) to a wide range of health outcomes in people with 'watch and wait' CLL, including cardiorespiratory fitness, strength, body composition, free-living physical activity levels, and wellbeing and physical function indices. Finally, this study will enable preliminary assessment of the changes (pre-intervention to post-intervention) to the potential anti-tumour mechanisms of exercise including immune function, inflammation, adipose tissue and metabolic hormones.

The hypotheses of this pilot study are as follows:

- Exercise will be safe and acceptable in people with 'watch and wait' CLL.
- Exercise will reduce the frequency of CLL tumour cells in the peripheral blood of people with 'watch and wait' CLL.
- Exercise will improve the cardiorespiratory fitness and the health and wellbeing of people with 'watch and wait' CLL.

Aims and outcomes

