The present trial will investigate the safety and acceptability of a 16-week home-based, progressive, exercise training intervention.

Primary objective:

1. Investigate the safety and acceptability of an exercise training intervention, in physically inactive people, with 'watch and wait' CLL.

Outcome measures, collected throughout the trial period:

- Safety (incidence and severity of adverse events)
- Uptake (proportion of people approached who attend screening, proportion of people who attend screening that are deemed eligible)
- Adherence (proportion of exercise sessions prescribed that are actually completed)
- Compliance (prescribed vs. actual aerobic exercise performed per exercise session)
- Retention (the proportion of participants who complete baseline measures that also complete follow-up measures)

Secondary objective:

1. Investigate the effect of an exercise training intervention on CLL disease activity, immune markers, overall fitness, health and wellbeing in physically inactive people, with 'watch and wait' CLL.

Outcome measures, collected pre- and post-trial period:

- Frequency of CLL cells in peripheral blood measured by flow cytometry
- Immune competency (e.g. phenotypic and functional analyses of PBMCs, differential blood count, viral infection history, immunoglobulins, complement proteins)
- Basal inflammation (e.g. cytokines)
- Metabolic factors and hormone levels (e.g. glucose, insulin, growth factors)
- Clonality of tumour cells (e.g., PCR).
- Genetic and epigenetic features of tumour and immune cells.
- Cardiorespiratory fitness (predicted, or VO_{2MAX})
- Body strength (measured by 1-rep max resistance exercises)
- Body composition (height, weight, waist and hip circumference, fat mass, lean mass)
- Wellbeing indices (stress, fatigue, sleep, quality of life, frailty, motivation, self-efficacy)
- Free-living physical activity levels via wearable technology (e.g., duration, intensity, frequency, energy expenditure and sedentary time)
- Physical function (e.g., flexibility, sit-to-stand test)
- Resting blood pressure, and heart rate
- Left ventricular (LV) function (volumes; ejection fraction; strain; diastolic function)
- Comparison of LV manual measures with artificial intelligence

Trial design

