Lactate threshold will be determined by plotting a graph of power in watts (x-axis) against the blood lactate in mM (y-axis). The definition of the blood lactate threshold as the break-point where a curvilinear rise in lactate concentrations is observed when plotted against power will then be used to determine the power at which the lactate threshold occurred. Work rates corresponding to -5%, +5% and +15% of the lactate threshold will be calculated from the lactate – to – work rate relationship. These work rates will then be used as the exercise intensities during the training intervention.

Health and safety: Participants unable to comply with the exercise test, for example due to a health problem raised during the exercise test (e.g. abnormal blood pressure response) or serious discomfort exercising, will discontinue involvement in the study on safety grounds. Abnormal test results will be referred to a cardiologist who will provide follow-up care and advice on the participants continued involvement in the trial. The decision on whether to repeat baseline measures will be discussed with the trial management group; e.g. if follow-up care results in a considerable delay, there may be a need to repeat baseline measures prior to commencing further trial activities.

Randomisation

Eligible, consenting participants will be randomly allocated (1:1) to an exercise training intervention (ETI) or standard care control (CON) group. Randomisation will be performed using a web-based platform.

Trial period measurements

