A final important consideration for the research team when designing this study was the global COVID-19 pandemic. To minimise this risk, the exercise training intervention has been designed to be conducted in participants homes. Appropriate personal protective equipment (PPE) will be worn by the research team during Visit 1, Visit 2 and Visit 3 and the study will adopt the policies that the Trust is following and will begin recruiting when the host institution allows it.

COVID-19 Mitigation Strategies

Given safety and institutional directives with the COVID-19 pandemic in the UK, the research team will adhere to the below policies and procedures:

• Any team member displaying any COVID-19 symptoms (fever (38°C or higher), or sense of having a fever, cough, shortness of breath, muscle aches, sore throat, unexplained loss of taste or smell, diarrhoea, headache) must stay at home and organise for a COVID-19 test by contacting their GP.

- Participants and research team will use hand sanitiser on entry to the University
- The research team will be provided with appropriate PPE (apron, gloves and a face covering/face mask and face shield throughout study participant visits)
- The research team will change gloves and apron between every study participant contact
- The research team will thoroughly wash hands and forearms before and after the session (not just use hand sanitiser)
- All research equipment will be wiped down immediately with disinfectant spray and cloth between study participant sessions
- Where possible staff will be vaccinated, and lateral flow tests will be done.
- Only two members of the research team will enter the participants homes to deliver the exercise equipment, and they will be in the home for no more than 15 minutes.

Statistics and data analysis

Sample size

The aim is to recruit 40 participants. Assuming a recruitment rate of three to four people per month and 20% drop out, we estimate the target can be reached within a suitable time-frame of the funding period (16-18 months).

There is limited information available to enable a formal sample size calculation. This pilot trial will provide preliminary data to determine that a future RCT has promise and is not futile, and to perform a sample size calculation.

Statistical analysis plan

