Primary outcome measures do not lend themselves to statistical analysis. Safety will be reported as the incidence and severity of adverse events. Acceptability will be reported as proportions in terms of uptake, adherence, compliance and retention.

Secondary data will be tested for normality (e.g. Shapiro-Wilk) and in the event that some data are not normally distributed, the data will be log transformed. Descriptive statistics will be presented, and longitudinal differences and interaction effects will be identified using repeated-measures T-tests. These data will be used to inform sample size calculations in a future RCT. Incomplete data and missing values will be managed using an intention-to-treat approach with multiple imputation.

The project may utilise correlation analysis to establish whether any change in disease activity is associated to a number of mechanistic markers, and stepwise multiple regression will identify the extent to which a change in the mechanistic markers predict change in disease activity. Subgroup analysis may be performed, e.g. split to high vs. low responders or by presence of mediating variable(s) for further analysis.

Monitoring, audit and inspection

The University of Bath, as Sponsor, will monitor and conduct random audits on a selection of studies in its clinical research portfolio. Monitoring and auditing will be conducted in accordance with the Department of Health Research Governance Framework for Health & Social Care (April, 2005), and in accordance with the Sponsor's monitoring and audit policies and procedures.

Patient safety will be monitored on an ongoing basis by the research and healthcare team. A formal data monitoring committee will not be convened as this is a small single-centre pilot study. Instead, the research team will present an update on safety at quarterly trial management group meetings, together with the haematologist ([name] and/or [name]), the CI ([name]), and patient representative(s).

Ethical and regulatory considerations

Research Ethics Committee (REC) review

Before the start of the trial, approval will be sought from an NHS REC for the trial protocol, informed consent forms, participant information sheet and recruitment letter. Substantial amendments will require review by the NHS REC will not be implemented until the NHS REC grants favourable opinion.

Public and patient involvement

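### Stepwise regression is named as the measure of how far marker changes predict disease activity, but its R-squared and p-values ignore the search and are biased upwards at about 32 completers

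*Protocol*

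**What the plan says.** Under Statistics and data analysis, the Statistical analysis plan subsection of the Protocol first allows for correlation analysis of whether change in disease activity is "associated to a number of mechanistic markers". The same sentence then says that "stepwise multiple regression will identify the extent to which a change in the mechanistic markers predict change in disease activity". So both the method and the quantity it is to deliver are stated.

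The marker list is open. Background and Summary names four mechanistic domains: "immune function, inflammation, adipose tissue and metabolic hormones". The secondary outcomes under Aims and outcomes fill these with families of measurements, for example "Immune competency (e.g. phenotypic and functional analyses of PBMCs, differential blood count, viral infection history, immunoglobulins, complement proteins", together with cytokines, glucose, insulin, growth factors and body composition measures. The Protocol sets no number of candidates, entry or removal threshold, limit on terms, or validation.

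On size, the Sample size subsection says "The aim is to recruit 40 participants" and continues "Assuming a recruitment rate of three to four people per month and 20% drop out". It adds that "There is limited information available to enable a formal sample size calculation". Missing values are to be multiply imputed.

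**The concern.** Stepwise regression picks the markers that happen to fit best in the sample and then reports R-squared and p-values as if those markers had been chosen beforehand. With few participants and several candidates, the winning marker is partly a chance winner. The reported fit is therefore too high on average, even when nothing is related to the tumour. The Protocol gives this method the task of measuring how far the markers predict disease activity, so the bias falls on the very quantity the analysis is meant to report.

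At stake is the credibility of the mechanistic result: which markers appear linked to disease activity, and how strongly. The usual output gives no warning, because a model built this way will look statistically significant.

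**Working it through.** **Inputs from the Protocol.** Recruitment target 40 and drop-out 20% (Sample size), so 40 × (1 − 0.20) = 32 completers. There is no formal sample size calculation, and no error rate or R-squared is stated for this regression, so there is no figure of the plan to reproduce.

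**Assumptions, because the Protocol does not give them.** Candidates k from 5 to 30. Two-sided entry at p<0.05 and removal at p>0.10, with looser entry as a sensitivity check. Markers independent, correlated in blocks, or all correlated at 0.5. All results are for the case where no marker is related to the outcome.

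**Step 1: chance of selecting something.** For independent candidates, forward selection starts whenever at least one single-marker test passes, so the chance is approximately 1 − 0.95^k. This gives 23% (k=5), 40% (10), 64% (20) and 79% (30). It first exceeds 50% at k=14: 1 − 0.95^13 = 48.7% and 1 − 0.95^14 = 51.2%.

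**Step 2: why the R-squared cannot be small.** With n=32 the first marker enters only if |t| > 2.042 on 30 degrees of freedom. Its R-squared is then at least t²/(t² + 30) = 4.170/34.170 = 0.12. At n=40 the floor is 4.098/42.098 = 0.10 (|t| > 2.024, 38 degrees of freedom). The entry rule itself guarantees a visible R-squared for whatever enters first.

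**Step 3: simulation of forward stepwise regression with backward removal, n=32.** Ranges span repeated runs, of 1,500 simulated trials per cell in the main run and 600 in another. At a rate near 50% the simulation standard error is √(0.25/1500) = 1.3 and √(0.25/600) = 2.0 percentage points.

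| k | Independent: at least one selected | Mean R² when selected | All correlated 0.5: at least one selected | Mean R² when selected |
|---|---|---|---|---|
| 5 | 22% | 0.19 | 18–20% | 0.19 |
| 10 | 41% | 0.22–0.23 | 29–30% | 0.22 |
| 20 | 64–67% | 0.27–0.29 | 42–47% | 0.27 |
| 30 | 76–81% | 0.34–0.36 | 50–52% | 0.33 |

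The true R-squared is 0 in every row. Adjusted R-squared does not cure this: with independent markers its mean after selection was 0.16, 0.18, 0.23 and 0.30 for k = 5, 10, 20 and 30, because it allows for the terms kept and not for those searched. The overall F test of the selected model was below 0.05 in every trial that selected a marker.

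**Step 4: sensitivity.**
- Markers correlated at 0.5 within blocks only: 42%, 51%, 54%, 65% and 71% for k = 12, 16, 20, 25 and 30, with mean R-squared 0.22 to 0.31. Applied to new data, the selected models had mean R-squared of −0.30 to −0.43, that is, they predicted worse than the mean.
- Entry at p<0.15, independent markers: 57%, 80% and 96% for k = 5, 10 and 20, with mean R-squared 0.16, 0.22 and 0.39. With all markers correlated at 0.5: 49%, 66% and 82%.
- AIC-like entry (p<0.157), blocks: 84% to 98% for k = 12 to 30, with mean R-squared 0.24 to 0.51.
- n=40, as if imputation restored everyone, p<0.05 entry, independent markers: 22%, 41%, 64% and 79% for k = 5, 10, 20 and 30, with mean R-squared 0.15, 0.17, 0.22 and 0.27.

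**Step 5: contrast with a pre-named model.** With three markers fixed in advance and no true association, the expected R-squared at n=32 is 3/31 = 0.10. The expected adjusted R-squared is 0, because no search has taken place.

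**The case against.** The strongest reply is about scope. The sentence opens in optional terms, the paragraph is exploratory, the mechanistic work is described elsewhere as preliminary, and the primary outcomes are only described. That limits the weight of the point but does not remove it. The regression clause itself is not optional in its wording, and the method and its purpose are stated in the Protocol, so this is not detail left to a separate analysis plan.

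A reader might infer that the procedure will usually find false predictors. The document does not support that without conditions. It gives no number of candidates and no entry rule, and nothing says that every measured analyte enters the model or that candidates approach the number of participants. At p<0.05 entry, 10 candidates give about 30% to 41%, and with all markers correlated at 0.5 it takes about 30 candidates to reach half of trials. A looser rule pushes the other way, so the rate is uncertain in both directions.

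A reader might also quote the more dramatic fit in the exercise arm alone. The Protocol does not restrict the regression to one arm, so such figures describe an analysis that is not planned. Nor does it say that the stepwise result will shape the future trial; the uses it states are a sample size calculation and a judgement of promise.

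Finally, penalised selection is not a full answer. In 200 null data sets per setting at n=32, a cross-validated lasso kept at least one marker in 44% (k=20), 38% (k=30) and 38% (k=20, correlation 0.5). Its cross-validated R-squared averaged about 0 when a marker was kept, so it corrects how strongly but not which marker. This objection stands and shapes the fix.

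**Conclusion.** The point holds in this form: the Protocol names a method whose R-squared and p-values are biased upwards for the purpose it states. In every setting tried at n=32, a selected model with no true association showed a mean R-squared of at least 0.16. At p<0.05 entry the figure was about 0.19 to 0.36 (about 0.15 to 0.27 at n=40 with independent markers).

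How often a false marker appears is a separate and less certain matter: about 22% to 78% for 5 to 30 independent candidates and about 18% to 50% if all are correlated at 0.5, higher under looser entry. These rates rest on assumed numbers of candidates, an assumed entry rule and no true association. If some markers truly matter, the reported fit would mix signal and selection noise in proportions that the document does not allow one to compute.

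The change should be made, but the point does not touch the safety and acceptability outcomes.

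**What to change.** Replace the stepwise procedure with a single model containing a few pre-named marker changes. About three suits 32 completers under the usual rule of thumb of 10 participants per term (32/10 ≈ 3). Report each estimate with its confidence interval, and an adjusted or optimism-corrected R-squared.

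If a wider set is explored, use ridge regression, or repeat the whole selection inside a bootstrap or cross-validation. Report only the validated R-squared, and label any selected markers hypothesis-generating.

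The cost is a changed sentence or two, a choice of markers before the data are seen, and somewhat more analysis work, including deciding how validation is combined with the planned multiple imputation. Fewer markers enter the main model and the reported R-squared will be lower. No extra participants, samples or visits are needed.

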IPAQ	International Physical Activity Questionnaire
iwCLL	International Workshop on Chronic Lymphocytic Leukaemia
LV	Left Ventricular
METs	Metabolic Equivalents
PARQ	Physical Activity Readiness Questionnaire
PBMC	Peripheral Blood Mononuclear Cells
PCR	Polymerase Chain Reaction
PIC	Participant Identification Centre
PSQI	Pittsburgh Sleep Quality Index
RCT	Randomised Controlled Trial
REC	Research Ethics Committee
RPE	Rating of Perceived Exertion
RUH	Royal United Hospital
SAE	Serious Adverse Event
VO_{2MAX}	Maximal oxygen uptake
WHO	World Health Organisation

Trial summary

mai summ	nar y						
Trial Title	Evaluating the safety and acceptability of a progressive exercise training intervention for Chronic Lymphocytic Leukaemia: a randomised-controlled pilot trial.						
Short title	Safety and acceptability of e	exercise for Chronic Lymphocytic Leukaemia.					
Clinical Phase Trial Design Trial Participants	I Pilot, single centre, randomised-controlled, phase I trial People diagnosed with Chronic Lymphocytic Leukaemia (CLL) will be invited to participate in this study. These people will be physically inactive and have asymptomatic early-stage CLL monitored without anti-CLL treatment, also known as 'watch and wait' CLL. Participants will be randomly allocated to either an exercise training intervention group, or a usual care control group.						
Planned Sample Size	Exercise training intervention n= 20 Usual care control group n= 20 Total sample size N= 40						
Intervention Duration	16 weeks						
	Objectives	Outcome Measures					
Primary	Objectives Investigate the safety and acceptability of an exercise training intervention, in physically inactive people, with asymptomatic early stage 'watch and wait' CLL.	 Outcome Measures The following will be assessed for safety and acceptability of exercise: Safety (incidence and severity of adverse events) Uptake (proportion of people approached who attend screening, proportion of people who attend screening that are deemed eligible) Adherence (proportion of exercise sessions prescribed that are actually completed) Compliance (prescribed vs. actual aerobic exercise performed per exercise session) Retention (the proportion of participants who complete follow-up measures) 					

	Investigate the effect of an	The following measurements will be collected
Secondary	exercise training intervention on CLL	to assess the effect of an exercise training intervention in participants with 'watch and

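### The optional split into high and low responders groups people on their own outcome change, and the alternative split on a mediator breaks the randomised comparison; subgroups should rest on baseline variables

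*Protocol*

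**What the plan says.** The last paragraph of the protocol's Statistical analysis plan section describes possible further work on the secondary data. Correlation analysis may be used to see "whether any change in disease activity is associated to a number of mechanistic markers". Stepwise regression is then to show "the extent to which a change in the mechanistic markers predict change in disease activity". The next sentence reads: "Subgroup analysis may be performed, e.g. split to high vs. low responders or by presence of mediating variable(s) for further analysis".

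These are the only two subgroup examples given. The section does not say which outcome defines response, what the cut-point is, or which arm would be split. It does not restrict subgroups to baseline variables, and the sentence does not label the splits as hypothesis-generating.

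Three other places fix the setting:
- Under Aims and outcomes, the secondary measures are headed "Outcome measures, collected pre- and post-trial period". The Trial flow chart shows blood tumour cell frequency at weeks 0 and 17 only.
- The Trial summary gives "Exercise training intervention n= 20 Usual care control group n= 20 Total sample size N= 40", and participants are "randomly allocated (1:1) to an exercise training intervention (ETI) or standard care control (CON) group".
- The Sample size section plans recruitment thus: "Assuming a recruitment rate of three to four people per month and 20% drop out".

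**The concern.** A subgroup of a randomised comparison has to be defined by something the intervention cannot have changed. As written, neither example meets that condition.

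**Responder split.** The preceding sentence is about change in disease activity, so that is the likeliest meaning of response. With one value before and one after, each person's change is a sum of true response, ordinary biological fluctuation and assay error. Cutting the sample on that sum gives a 'high' and a 'low' group in any data set, and the control arm would give them too. Because a high baseline reading tends to be followed by a lower one, the group with the largest fall will also tend to have started higher.

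**Mediator split.** A mediator is by definition affected by the intervention, and the preceding sentence speaks of change in the markers. Comparing arms within levels of such a variable compares people who are no longer exchangeable. This fault differs from the responder artefact. Its size depends on how far marker and outcome share causes.

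At stake is the reading of the secondary results. The protocol wants the pilot to show whether a larger trial has promise. A 'responder' half with a significant fall in CLL cells, or a 'responder' profile with higher baseline load, could be taken as evidence of promise when it is produced by the split.

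**Working it through.** The protocol gives no figure for this analysis and no formal sample size calculation, so there is nothing of its own to reproduce. The check asks what the split yields when everyone's true response is the same.

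**Inputs from the protocol**
- 20 per arm (Trial summary) and 20% drop-out (Sample size): 20 × 0.8 = 16 completers in the exercise arm, so 8 per half after a median split.
- One value before and one after per person (Aims and outcomes; Trial flow chart).

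**Assumptions, because the protocol gives none of these**
- Normal data with equal SD at both visits, a median split, and two-sided tests at 0.05.
- Test-retest correlation r of 0.9, 0.8 or 0.7.

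**Step 1. Gap in change between the halves.** With n = 16, the two halves of an ordered normal sample differ on average by 1.52 SD of change (simulated). This gap comes from the sorting itself.

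**Step 2. Spurious baseline gap.** Let B be baseline and F follow-up, each with SD 1, and C = F − B.
- Var(C) = 2(1 − r) and Cov(B, C) = −(1 − r).
- Corr(B, C) = −(1 − r)/√(2(1 − r)) = −√((1 − r)/2).
- Expected baseline gap = 1.52 × √((1 − r)/2).

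| r | √((1 − r)/2) | Baseline gap (SD) | Gap falsely significant (simulated) |
|---|---|---|---|
| 0.9 | 0.224 | 1.52 × 0.224 = 0.34 | about 10% |
| 0.8 | 0.316 | 1.52 × 0.316 = 0.48 | about 15% |
| 0.7 | 0.387 | 1.52 × 0.387 = 0.59 | about 21% |

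The nominal rate is 5%. The group with the larger fall is the one that starts higher. Simulating the baseline gaps directly agrees with the formula to within about 0.01 SD.

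**Step 3. Pre-post test inside the 'high' half.** With zero true effect, a one-sample t-test of change in the 8 'high responders' is significant in about 81% of runs. The 'low' half is significant in the opposite direction equally often. With all 20 retained the figure is 90%.

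**Step 4. Mediator split.** Here exercise has no effect on the outcome but shifts the marker by 0.8 to 1.2 SD. Marker and outcome share an unmeasured cause, with an assumed loading of 0.5 to 0.7 on each. The arms are compared within the high-marker half, with 16 or 20 per arm.
- Unsplit arm comparison: error rate about 5%, as it should be.
- Within the high-marker half: bias of −0.13 to −0.37 SD, rejection in about 5 to 11% of trials.

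The bias is real, but it rests wholly on the assumed loadings, and the excess of false positives is modest at this sample size.

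**Step 5. Can the data show that response varies at all?** The natural check is whether change varies more in the exercise arm than in the control arm. With 16 per arm and no individual response, the difference in variances is negative in about 50% of trials. When the SD of individual response is half the control-arm SD of change, it is still negative in about 34%, and a one-sided variance-ratio test at 0.05 has about 11% power. The comparison is valid but very imprecise here.

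**The case against.** The strongest answer is that the sentence is permissive and illustrative. It concerns possible further work on secondary data in a pilot whose primary outcomes are descriptive. The Background frames the mechanistic aim as "preliminary assessment of the changes (pre-intervention to post-intervention) to the potential anti-tumour mechanisms of exercise"; that passage says nothing about subgroups, but it does set a cautious tone. No hypothesis, sample size statement or stated decision depends on the split. This stands, and it limits the severity.

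A second answer is that response is undefined. It could mean fitness response, and a definition may sit in an analysis plan not shown here. It is true that disease activity is only the likeliest reading. If groups were formed on fitness, the figures in steps 1 to 3 would describe fitness rather than tumour load. The split would still be on something measured after randomisation. Likewise, 'mediating' may be loose wording for a baseline moderator. If so, the same edit makes that clear.

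Three stronger readings are tempting and are not supported:
- A reader might infer that the trial will nearly always report a false finding, because the halves differ significantly in change in 100% of simulated runs. That figure only tests the halves on the variable used to form them, and the protocol does not propose that test. The baseline gap and the test within the 'high' half are the informative results.
- A reader might infer that a mediator split also creates responders out of nothing. It does not; its fault is a biased comparison between arms.
- A reader might infer that responder profiles would decide who enters the next trial. The protocol names only a sample size calculation and a judgement of promise as later uses.

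**Conclusion.** The point holds as a fault in what the protocol states, rather than as detail left to another document. If the responder split is made on change in disease activity, it conditions on the outcome and cannot tell individual response from noise. With 16 completers, identical true response and a median split, expect a spurious baseline gap of 0.34 to 0.59 SD, falsely significant in about 10 to 21% of trials. With no effect at all, expect a significant change in the 'high' half in about 81%. The baseline figures rest on assumed test-retest correlations of 0.9 to 0.7. All of them rest on normal data, the assumed cut-point and the reading of response given above.

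The mediator split is a separate fault, conditional on 'mediating' meaning a change in a marker. Its size cannot be fixed from the protocol.

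Severity is minor to moderate: the analysis is optional, and safety and acceptability do not rest on it.

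**What to change.** Replace the subgroup sentence in the Statistical analysis plan section. Suggested content:
- Subgroups are defined only by variables fixed before randomisation, for example baseline CLL count, age, sex or baseline fitness.
- Each is reported as an arm-by-variable interaction with a confidence interval and labelled exploratory.
- Change in disease activity stays continuous; participants are not sorted into responder groups or by a variable measured after randomisation.

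If variation in response is of interest, the SD of change may be compared between arms as a descriptive check with its interval, stating that it is very imprecise at about 16 per arm.

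The cost is one sentence and no new data. The downside is that interaction estimates from about 32 completers will be wide, and no 'responder' groups can be reported.
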